# Sample Size

The sample size is based on the study by Suntrup et al., which documented wide variability in ketone measurements during the day in persons undergoing dietary modification to enhance ketogenesis, also in the control group. In that study of 21 participants, over 1000 paired measurements were generated to determine the correlation between BrAce with BOHB using the Precision Xtra ketone meter, providing R^2 =0.57. Further analysis demonstrated receiver operating characteristic curves with AUC  $\geq$ 0.80 for values of BOHB at the 0.5 mM and 1.0 mM thresholds. This study will generate ~1400 paired measurements, which are expected to be in the same range during usual care and usual care plus SGLT2i. Since the main objective of the study is to determine whether the Biosense BKA provides sufficient information for the patient to consider action steps to avoid worsening ketosis, the ROC analysis is crucial and the

number of observations needed is expected to be about 1000. For the insulin withdrawal studies, a difference of BOHB levels of 1.0 mmol/L between usual care and usual care plus dapagliflozin, a sample size of 16 completing both study days can be detected with 80% power and two sided significance level of 5%.

#### Data Management and Analysis

Participants will be assigned a randomly generated patient ID number, not in order of participation. All data will be entered into a dedicated Redcap database without patient identifiers for analysis. Baseline cohort information will include demographic information, diabetes duration, history of last DKA episode, complications, eGFR and insulin doses during usual care and at the end of the usual care + SGLT2i therapy. Glucose parameters, including time in range, time above and below range will be recorded at the end of each 2-week segments from CGM downloads during the usual care and usual care + SGLT2i study segments. Capillary BOHB measurements and BrAce levels will be paired, and only those taken within a 1 hour window will be entered as data during the usual care and usual care + SGLT2i (study segments 1 and 2). Data entry for on-site insulin-withdrawal visits will include patient vitals and weight, all laboratory values, hourly paired capillary BOHB and BrAce levels with laboratory BOHB and AcAc. Adverse events during the study will be manually tabulated.

The study will be monitored for data integerity by an uninvolved study coordinator or fellow within the division to check for errors, omissions and to generate a report to the DSMB.

Data analysis will be done using SAS through either the WU CTSA Statistics center or a faculty member in the division with SAS capability.

#### Assessment of Efficacy

The main efficacy parameter will be the correlation between BrAce levels and capillary blood BOHB levels during segments 1 and 2, usual care and usual care + SGLT2i of the study using linear regression. Efficacy will be established with  $R^2 > 0.6$ . Separate linear regressions will determine the correlation of BrAce levels with capillary blood BOHB, of BrAce levels and laboratory BOHB, and of BrAce levels and AcAc. Efficacy of BrAce for correctly indicating actionable ketosis will be established with  $R^2 > 0.6$ . Additionally, a receiver operating characteristic (ROC) analysis will be performed to clarify the diagnostic ability of BrAce compared to capillary blood BOHB to correctly or incorrectly identify ketone levels that would be considered actionable for a person with T1D, or >1.5 mmol/L.

Qualitative analysis will be undertaken based on a simple Likert scale questionnaire with the following questions rated from 1 to 5:

- Did testing breath ketones help you to understand your "ketone status"?
- Were you able to identify episodes of mild ketosis with the Biosense breath ketone analyzer?
- Are you likely to continue to use the Biosense breath ketone analyzer for this purpose?

The main efficacy parameter will be assessed with an interim analysis after completion of 12 subjects in the trial, with results reported to the DSMB and to the funding partner, JDRF. Adverse events will be manually tabulated and reported.

#### Assessment of Safety

Safety parameters will be analyzed separately for the usual care segments and for the insulin withdrawal days. For the usual care segment, the main safety concern is a level of capillary blood BOHB >1.5 mmol/L at any time. Participants will be asked to call the study coordinator or investigator for advice if this happens, and to start a ketone action plan. The participant can call for concerns about any level of capillary BOHB during the study, but in particular while taking an SGLT2i. The participant will be

provided with a ketone-action plan that will include ingestion of carbohydrates, fluid and insulin administration and frequent follow-up testing. The study investigator will monitor the participant with contact every 1 - 2 hours until the episode resolves. Any capillary blood BOHB level >1.5 mmol/L will be reported as an event of special interest, with follow-up ketone action plan results noted. BrACE levels of >15 without corresponding BOHB level >1.0 mmol/L will be considered likely due to contamination and repeated in 1 hour. Likewise, any severe hypoglycemia event will be reported as an adverse event. Patients with level 2 hypoglycemia, glucoses <54 mg/dL for more then 1% of the day on weekly CGM reviews will have insulin doses adjusted and a discussion with the investigator.

The most important safety parameter of the insulin withdrawal test days will be capillary blood BOHB levels >3 mmol/L, or symptoms of nausea or vomiting at any level of BOHB. Capillary BOHB level of >3 mmol/L constitutes a stopping point for the insulin withdrawal study, and immediate treatment with fluids, insulin and carbohydrates will be commenced, and the patient followed on-site until the episode resolves. Resolution will be defined as cessation of symptoms and capillary BOHB level <1.0 mmol/L, with blood glucose <250 mg/dL. Note that in a similar study of insulin withdrawal before and after treatment with the SGLT2i, canagliflozin, it took about 6 hours for glucose to increase from 100 to 300 mg/dl (pre-treatment) and from 100 to 220 mg/dL with canagliflozin. During the six hours, BOHB increased from 0.2 to 1.2 mmol/L (pre-treatment) and from 0.4 to 1.5 mmol/L with canagliflozin. This proposal uses a similar time sequence, and thus we anticipate similar results from the insulin withdrawal.

Other adverse events, such as genital mycotic infections, urinary tract infections, orthostatic dizziness or any other acute or worsening illness will be reported. Study fatigue resulting in termination of the study will also be reported.

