After the investigator or sub-investigator determines that the participant meets all of the inclusion and none of the exclusion criteria, the study team will proceed with interrogation of the participant's CGM to ensure appropriate connectivity with the study team. Participants will be asked to demonstrate competency in making changes to insulin pump settings. The study team members will train the participant in the use of the Precision Xtra ketone meter and the Biosense BKA. Participants will be instructed to wait 60 minutes after eating, smoking/vaping, drinking sodas or flavored waters or consuming items such as toothpaste, mouthwash, cough drops, breath mints, chewing gum, lip balm and artificial sweeteners before doing a BrACE measurement. If using alcohol, participants should wait 4 hours before testing with the BKA. Participants will be instructed in avoidance of environmental contaminants also. Participants will be able to test capillary BOHB even when conditions are not optimal for BrACE.

The participant will upload the Biosense app onto his or her smart phone and test a test run will be conducted. A diary will be provided for entry of BOHB ketone measurements and BrAce with space for comments in case of known interference with BrAce or other problems with measurements. A written ketone action plan will be provided to all participants in the study. Participants will be informed that they may stop participating in the study at any time without loss of usual care of their diabetes.

A ketone action plan will be provided to each participant that will include the following elements: ingestion of carbohydrates, fluid intake and insulin administration with doses of insulin adjusted according to individual requirements. Participants will be asked to employ the ketone action plan if BOHB reading is >1.5 mmol/L. BrACE levels of >15 in the absence of corresponding BOHB level >1.5 mmol will be considered due to contamination and the participant will be asked to repeat the levels in 1 - 2 hours.

Patients will be randomized by card draw in lots of 4 to Group A or Group B

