#### On-site Visit

The on-site will be conducted at the Intensive Research Unit at Washington University. Patients will be asked to arrive fasting, to stop their basal insulin delivery 1 hour before arrival at the center if on an insulin pump or to hold injectable insulin doses. Prior to leaving home, the participant's blood glucose should be 90 – 250 mg/dL, and BOHB <1.5 mmol/L, or the test day will be rescheduled. Time of the last insulin dose will be recorded. Vital signs and baseline labs including a CBC, BMP and pregnancy test in women with child-bearing potential will be done. Measurements of capillary BOHB using the Precision Xtra meter and BrACE using the Biosense BKA will be done hourly X7 or 8 if the patient remains relatively asymptomatic, and the capillary BOHB level does not exceed 4 mmol/L. If the capillary BOHB reaches 2.5 mmol/L or capillary glucose reaches 250 mg/dL, the capillary finger sticks and breath measurements may be collected at 30 minute intervals. The venous blood samples will continue to be collected on the hour intervals. Venous blood samples for BMP, BOHB and AcAc\* will be drawn at baseline and every 2 hours X3 plus the end of the study.

The insulin withdrawal portion of the study will end (stopping rules) upon patient request for any reason, if the patient becomes symptomatic with nausea or vomiting (even if he or she does not request that the study be stopped), after 7 hours of fasting without insulin, or if either the capillary BOHB is  $\geq$ 4 mmol/L or the CGM blood glucose is  $\geq$ 400 mg/dL. BMP will be done every 2 hours and at the end of the study. At the termination of the ketogenic fast, participants will be given a correction dose of rapid acting insulin subcutaneously or regular insulin IV, per investigator discretion. They will then restart insulin via insulin pump, or administer both basal and mealtime insulin via subcutaneous injection and be given a standard meal. Participants will be observed for a minimum of 1 hour after the study end for return to near normal metabolic status. An additional contact by phone or other means in the evening will be made to confirm safety and no adverse consequences of the study day.

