# Summary of protocol changes

10Jan2023 – Updated stopping rules for on-site visits: blood ketone  $\geq$  4mmol/L or glucose  $\geq$  400 mg/dL. This does not present an increase in risk/benefit for participants. Finger sticks for glucose/ketone monitoring may be collected every 30 minutes to 1 hour for the duration of the study.

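### The insulin-withdrawal day has two capillary BOHB stopping limits in current text: at least 4 mmol/L in the visit procedures, above 3 mmol/L in the safety section

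*Combined protocol and SAP*

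**What the plan says.** The combined protocol and SAP sets the withdrawal-day limits in three places.

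- **On-site Visit (usual care).** Hourly capillary and breath measurements go on while the participant is relatively well and "the capillary BOHB level does not exceed 4 mmol/L". The list labelled as stopping rules then ends withdrawal on patient request, on nausea or vomiting, "after 7 hours of fasting without insulin, or if either the capillary BOHB is" at least 4 mmol/L, or if CGM glucose is at least 400 mg/dL. Capillary and breath checks may move to every 30 minutes once BOHB reaches 2.5 mmol/L or capillary glucose reaches 250 mg/dL.
- **On-site visit, SGLT2i.** The same limits are repeated.
- **Assessment of Safety.** BOHB above 3 mmol/L, or nausea or vomiting at any BOHB, is named as the leading safety parameter of these days. The text continues: "Capillary BOHB level of >3 mmol/L constitutes a stopping point for the insulin withdrawal study, and immediate treatment with fluids, insulin and carbohydrates" are then to be started. This section has no glucose stop at 400 mg/dL.

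The Summary of protocol changes, dated 10 January 2023, records: "Updated stopping rules for on-site visits: blood ketone" at least 4 mmol/L or glucose at least 400 mg/dL.

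**The concern.** The two limits apply to the same analyte, sample type and procedure, and both are called stopping criteria. They cannot be read as an alert level and a stop level, because the safety section orders treatment at its limit and the visit sections already have a separate step-up level at 2.5 mmol/L.

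The trial deliberately withdraws insulin from people with type 1 diabetes, once while they are taking a drug for which the Rationale reports two to three times the placebo incidence of DKA. Staff who follow the visit procedures would carry on past the level that the safety section treats as most important. Staff who follow the safety section would end the test earlier than the visit procedures require. Either way they depart from part of the protocol. The DSMB and the consent form, which is to describe the stopping rules, both need a single rule.

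**Working it through.** **Step 1. Compare the rules by BOHB reading in a participant without symptoms and with glucose below 400 mg/dL.**

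| Capillary BOHB (mmol/L) | On-site visit sections | Assessment of Safety |
|---|---|---|
| up to 3 | continue | continue |
| above 3, below 4 | continue | stop and treat |
| 4 or more | stop | stop and treat |

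The middle row is the contradiction. Nothing in the document says which section governs. The change log is not a precedence clause. It is used here only as evidence of intent: it gives the same 4 and 400 as the visit sections, and the safety section contains neither value. The log does not state the previous limit, so it is an inference that the 3 mmol/L sentence is a leftover.

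**Step 2. How often might the band be reached?** The safety section anticipates results like those of an earlier canagliflozin study, in which over six hours "BOHB increased from 0.2 to 1.2 mmol/L (pre-treatment) and from 0.4 to 1.5 mmol/L with canagliflozin".

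- Usual-care slope: (1.2 − 0.2)/6 = 0.167 mmol/L per hour. Level at 7 h: 0.2 + 7 × 0.167 = 1.37.
- SGLT2i slope: (1.5 − 0.4)/6 = 0.183 mmol/L per hour. Level at 7 h: 0.4 + 7 × 0.183 = 1.68.
- Slope needed to pass 3 by 7 h: (3 − 0.2)/7 = 0.400 (usual care); (3 − 0.4)/7 = 0.371 (SGLT2i).
- Slope needed to reach 4 by 7 h: (4 − 0.2)/7 = 0.543; (4 − 0.4)/7 = 0.514.

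The typical participant therefore stays well below 3. The share in the upper tail depends on the between-person SD of the slope, which the protocol does not give. **Assumed** SDs are 0.06, 0.12 and 0.18 mmol/L per hour. With a linear rise and slopes normal but truncated at zero,

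P(pass 3) = [1 − Φ((needed − mean)/SD)] / Φ(mean/SD).

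For example, on the SGLT2i day with SD 0.12: [1 − Φ((0.371 − 0.183)/0.12)] / Φ(0.183/0.12) = 0.0585/0.937 = 6.2%.

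| Scenario | SD 0.06 | SD 0.12 | SD 0.18 |
|---|---|---|---|
| Usual-care day, start 0.2, mean 0.167 | 0.0% | 2.8% | 11.8% |
| SGLT2i day, start 0.4, mean 0.183 | 0.1% | 6.2% | 17.5% |
| SGLT2i day ending 1.0 above usual care, start 0.4, mean 0.281 | 6.6% | 22.8% | 32.7% |

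Of 20 participants, the SGLT2i row is about 0, 1 and 3 to 4 people. The last row takes from the Sample Size section "a difference of BOHB levels of 1.0 mmol/L between usual care and usual care plus dapagliflozin": 1.37 + 1.0 = 2.37 at 7 h, so the slope is (2.37 − 0.4)/7 = 0.281. That is the difference the study is sized to detect. The safety section itself anticipates only 1.5 − 1.2 = 0.3 at six hours.

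**Step 3. Does the choice of limit change the planned analysis of BOHB against time?** The pooled least-squares slope was simulated for 20 participants read hourly from 0 to 7 h, keeping the reading that triggers the stop.

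| SGLT2i day, start 0.4, nominal mean 0.183 | SD 0.06 | SD 0.12 | SD 0.18 |
|---|---|---|---|
| Stop above 3 | 0.183 | 0.196 | 0.214 |
| Stop at 4 | 0.183 | 0.200 | 0.232 |

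Truncation at zero lifts the realised mean slope above nominal at the wider SDs (0.200 and 0.235 with no cap), so compare the two rows with each other and not with 0.183. In the scenario ending 1.0 higher, at the widest SD, the slopes are 0.258 and 0.293.

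The primary outcome is the usual-care home correlation and is not touched. Any reading between 3 and 4 is above 1.5 mmol/L and so is ROC-positive under either rule.

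**Step 4. A smaller mismatch of the same kind.** The Visit 1 text says "BrACE levels of >15 in the absence of corresponding BOHB level >1.5 mmol will be considered due to contamination", and the ketone action plan under On-site Visit repeats it. Assessment of Safety says "BrACE levels of >15 without corresponding BOHB level >1.0 mmol/L will be considered likely due to contamination". A BrACE above 15 with BOHB above 1.0 and up to 1.5 mmol/L is thus contamination under one rule and not under the other.

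**The case against.** The strongest reply is that the practical risk is bounded. Nausea or vomiting ends the test at any BOHB, glucose of 400 mg/dL ends it too, physician oversight is scheduled, and 30-minute checks are allowed from 2.5 mmol/L, which covers the disputed band. The two visit sections agree with each other and with the latest dated change, so this is arguably one stale sentence. All of that is fair, and it lowers the likely harm. It does not give an asymptomatic participant at, say, 3.4 mmol/L a single rule. The 30-minute checks are optional and would only show the conflict sooner.

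The frequency figures are also open to challenge. The SDs are assumed, and truncation raises the mean. A gamma distribution that keeps the mean, at SD 0.18, gives about 13% instead of 17.5% on the SGLT2i day, and about 25% instead of 32.7% in the scenario ending 1.0 higher. Stops for glucose, symptoms or patient request are left out; at the anticipated usual-care rate, glucose would be near 100 + 7 × (200/6) = 333 mg/dL at 7 h, so some participants could stop on glucose first. These points stand. The shares are illustrations, and the contradiction does not depend on them.

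At a reading of exactly 4.0, the measurement condition (not exceeding 4) and the stopping rule (at least 4) point different ways, but the explicit stopping rule settles it. That is tidying only.

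**Conclusion.** The concern holds, and the text must be corrected. Current sections give opposite instructions for every capillary BOHB above 3 and below 4 mmol/L on the withdrawal days. This follows from the text alone and needs no assumption.

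Probably only a minority would enter the band: about 0% to 17% on the SGLT2i day at the anticipated mean rise, and up to about a third if that day ends 1.0 mmol/L higher. Both ranges rest on assumed SDs and a linear rise. The statistical effect is none on the primary outcome, none on ROC classification, and negligible to small on the BOHB-time slope at the anticipated rise. The reason to act is participant safety and a definable standard of compliance. That 4 mmol/L is the intended limit is likely from the change log but is for the investigators to confirm.

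**What to change.** 1. Put one BOHB and glucose stopping rule, in identical words, in On-site Visit, On-site visit, SGLT2i, and Assessment of Safety. If the January 2023 update stands, that is BOHB of at least 4 mmol/L or glucose of at least 400 mg/dL. Have the investigators and the DSMB confirm it.
2. State in Assessment of Safety whether a level above 3 mmol/L is kept as an alert or reporting level and, if so, what staff do when it is reached.
3. Word the condition for continuing measurements as BOHB below 4, so that it matches the stop.
4. Choose one BOHB cut-off, 1.5 or 1.0 mmol/L, for treating BrACE above 15 as contamination, and use it in all three places.

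The cost is a text amendment: one sentence in the safety section, matching wording in the two visit sections, and one number for the contamination rule. No extra data or visits are needed.

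### The 80% power claim for the insulin-withdrawal comparison rests on an unsupported 1.0 mmol/L BOHB difference, while the protocol's own anticipated results imply about 0.3 mmol/L

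*Combined protocol and SAP*

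**What the plan says.** The only power statement for the withdrawal days is at the end of the Sample Size section. It refers to "a difference of BOHB levels of 1.0 mmol/L between usual care and usual care plus dapagliflozin", and says that this, with "a sample size of 16 completing both study days", "can be detected with 80% power and two sided significance level of 5" per cent. The section does not give the SD of the within-person difference, the hour at which BOHB is compared, whether BOHB is capillary or venous, or where 1.0 comes from. Enrolment is 20 (Rationale).

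The Assessment of Safety section gives the documents' only BOHB figures from an insulin-withdrawal study with and without an SGLT2i. Over six hours, "BOHB increased from 0.2 to 1.2 mmol/L (pre-treatment) and from 0.4 to 1.5 mmol/L with canagliflozin". It continues: "This proposal uses a similar time sequence, and thus we anticipate similar results from the insulin withdrawal". In this trial each withdrawal day ends at the latest "after 7 hours of fasting without insulin" (On-site Visit; the SGLT2i visit has the same limit).

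Objective 3 includes the hypothesis that the SGLT2i raises blood and breath ketones during insulin deficiency. For the SGLT2i effect on withdrawal days, the Statistics section plans an extra sum-of-squares F test on the slope and intercept of capillary BOHB against time, and Fisher's exact test on the frequency of venous BOHB above 1.5 mmol/L. It plans no within-person comparison of BOHB level between the two days.

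**The concern.** The two sections do not fit together. The difference used for power is more than three times the end-level difference in the study whose results the protocol expects to resemble, and it equals the whole six-hour rise seen there without drug (0.2 to 1.2 mmol/L).

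A detectable difference supports a sample size only if it is plausible, or is argued to be the smallest difference that matters. The Sample Size section argues neither. A reader who takes the 80% at face value will think the SGLT2i part of objective 3 is well powered. Nothing in the documents lets anyone confirm that, and the protocol's own expectation points the other way unless the within-person SD is small.

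**Working it through.** **Inputs from the documents**

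- Powered difference 1.0 mmol/L, 16 completers, 80% power, two-sided 5% (Sample Size).
- End levels at 6 hours: 1.2 mmol/L without SGLT2i, 1.5 with it (Assessment of Safety).
- Enrolment 20 (Rationale); withdrawal limit 7 hours (On-site Visit).
- SD of the within-person difference: not stated. It is solved for below and then varied as an assumption.

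**Step 1: what the stated claim implies.** The claim cannot be reproduced without an SD, so it is solved backwards. For a paired t-test with n = 16 (15 degrees of freedom, critical value 2.131), power is the probability that a noncentral t variable with noncentrality (difference / SD) × √n falls outside ±2.131. Power of 80% needs difference / SD = 0.749, so

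SD = 1.0 / 0.749 = 1.33 mmol/L.

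The normal approximation gives √16 / (1.960 + 0.842) = 1.43 mmol/L.

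**Step 2: the difference the protocol anticipates.**

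- At 6 hours: 1.5 − 1.2 = 0.3 mmol/L.
- Extended linearly to 7 hours: without drug 0.2 + (1.0/6) × 7 = 1.37; with drug 0.4 + (1.1/6) × 7 = 1.68; gap 0.32 mmol/L.
- Ratio of powered to anticipated difference: 1.0 / 0.3 = 3.3.

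The seventh hour makes almost no difference.

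**Step 3: power for 0.3 at the implied SD.** Noncentrality with 16 completers is (0.3 / 1.334) × 4 = 0.90. Power is 13%. If all 20 complete, it is 16%. The normal approximation with its own implied SD also gives 13% for 16 completers.

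**Step 4: range over the unknown SD.** Power for 0.3 mmol/L with 16 completers, same paired t-test:

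| Assumed SD of differences (mmol/L) | Power |
|---|---|
| 0.40 | 80% |
| 0.6 | 46% |
| 1.0 | 20% |
| 1.33 (implied by the claim) | 13% |
| 2.0 | 9% |

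For 16 completers to have 80% power at 0.3, the SD must be about 0.3 / 0.749 = 0.40 mmol/L, under a third of the value the claim implies.

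**Step 5: precision.** At SD 1.33 the 95% interval for the mean difference has half-width 2.131 × 1.334 / √16 = 0.71 mmol/L, more than twice the anticipated 0.3.

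**The case against.** Five points deserve weight.

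- **1.0 is worded as a detectable difference, not an expected one.** This stands. The power statement is not arithmetically wrong and does not formally contradict a smaller expectation. It still lacks any justification for 1.0.
- **The 0.3 comes from a different drug and from a safety section.** This stands in part. The Rationale says the design is also patterned on a dapagliflozin withdrawal study, and dapagliflozin is the drug given here. That study's BOHB values are not in the documents, so it may support 1.0. But the protocol does say that it anticipates results similar to the canagliflozin study.
- **The 13% uses an SD solved from the very claim in dispute.** This stands. Power at 0.3 is strictly unknown, and the range in Step 4 should be quoted with the 13%.
- **A paired t-test is not the planned analysis.** This stands. The power statement corresponds to no analysis in the Statistics section, which is a further reason to reconcile the two.
- **This is a secondary comparison.** This stands. The primary outcome is the correlation of breath acetone with capillary BOHB during usual care, and objective 3 also has a correlation part that needs no gap between the days.

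A reader might also infer that the withdrawal day is too short to show an SGLT2i effect. The documents do not support that. On the quoted figures the gap starts at 0.2 and widens by 0.1 / 6 = 0.017 mmol/L per hour, so the limit of 7 hours is not what separates 0.3 from 1.0. Nor do they support computing power on the difference in rise (1.1 − 1.0 = 0.1), because the plan names no change-from-baseline endpoint.

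**Conclusion.** The concern holds as a point about an unsupported power statement. The 80% is tied to a difference with no SD, time point or source, and the only figures in the documents suggest a difference of about 0.3 mmol/L. At the SD the claim implies, power for 0.3 is about 13% with 16 completers and 16% with 20. Across assumed SDs of 0.40 to 2.0 it runs from 80% down to 9% with 16 completers.

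This rests on three assumptions: a paired comparison of level at one time point, end levels like those of the canagliflozin study, and an SD that the documents leave open.

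It would go too far to say that the design certainly lacks power, because a small SD or a larger dapagliflozin effect cannot be excluded. It would also go too far to say that the trial will present a null result as reassurance. The documents do not say so, and Research Design already treats the SGLT2i increase in ketones as demonstrated.

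**What to change.** 1. In Sample Size, state the SD of the within-person difference, the time point, whether BOHB is capillary or venous, and the source for 1.0 mmol/L. The dapagliflozin withdrawal study cited in the Rationale could serve, if its figures support 1.0.
2. If no source supports 1.0, restate the power at the roughly 0.3 mmol/L implied by Assessment of Safety, with a range over plausible SDs, and drop the 80% claim for the withdrawal comparison.
3. In Statistics, add the within-person difference in BOHB between the two withdrawal days at the named time point, reported with a 95% interval. State how a day that ends before that time point enters the comparison.
4. State that a non-significant result will not be interpreted as absence of an SGLT2i effect.

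The withdrawal duration and the number enrolled need no change. The cost is a less favourable stated power and one small added analysis of data already being collected.
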